**PROMIS – kysely arpityräriskin arvioimiseksi**

1. Uskotko, että Sinulla voi olla

arpityrä?

Kyllä

Ei

2. Tunnetko kipua arvessa?

PREEMER TRIAL 24

Kyllä

Ei

3. Onko arvessa pullotusta tai pattia?

Kyllä

Ei

4. Näkyykö arvessa pullostusta tai pattia?

Kyllä

Ei

5. Painosi?

\_\_\_\_\_ kg

6. Pituutesi?

\_\_\_\_\_ cm

7. Tupakoitko, tai oletko koskaan tupakoinut

päivittäin?

Kyllä

Ei

## 12. Schedule of Events

Schedule of Events	Baseline	Procedure	Discharge	30 days + 7 days	2 year ± 30 days	5 years ± 30 days	Unscheduled Visit
Informed Consent	X						
Demographics and medical history	X						
Risk analysis for hernia	X						
QoL (RAND-36, AAS, PROMIS)			X	X	X	X	

Procedure details		X					
Clinical evaluation	X		X	X	X	X	X
Ultrasound findings					X	(X*)	(X)
Protocol Deviation	X*	X*	X*	X*	X*	X*	X*
Complications		X*	X*	X*	X*	X*	X*
Study Closure Form						X**	

\*Complete if applicable

\*\*Complete when lost to follow-up, consent withdrawal or subject has completed all study related visits.

### 13. Subject Withdrawal and Discontinuation

The subject's participation in any clinical trial is voluntary. The subject and/or the representative of subject has the right to withdraw at any time without penalty or loss of benefit. Study

withdrawal means the subject is no longer participating in the study and no further study-related follow-ups will be performed. All subjects that withdraw after informed consent is signed will be evaluated at the time of withdrawal. Every effort will be made to document the subject outcome at the time of withdrawal. Data collected until withdrawal will be analyzed. The investigator has the right to discontinue subjects from the study at his/her discretion to ensure wellbeing of the subject. The reasons for withdrawal shall be documented (electronic Patient Withdrawal Request Form).

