### 10.3. Study Plan

[figure not shown]
*Figure 1 Flow Chart*

Intend to treat population  
reaching 30 days control

Intent to treat  
population  
reaching 2 years  
control

Intent to treat  
population  
reaching 5 years  
control

Data will be collected at baseline, operative procedure, discharge, 30 days, 2 years and 5 years. Specific databases (Hoitoilmoitusrekisteri HILMO, Tilastokeskus) may be used to collect data of patients' survival and operations done to patient outside study sites. If there is any suspicion of

PREEMER TRIAL 17

incisional hernia raised at any point of the follow-up, the patient is advised to contact the study site and additional clinical evaluation and ultrasonography if needed is arranged. The data will be collected using electronical CRFs and software designed for this study.

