#### 13.1 Subject lost to Follow-up

The investigator will attempt to contact the subject at least three times prior to designating them as lost to follow-up. The patient who may hesitate to come to follow-up visit, are asked to return the PROMIS questionnaire to estimate the risk of incisional hernia (48).

The investigator will

document the date and type of attempted communication. If a subject cannot be reached during the visit window, a missed visit will be recorded. Each patient in the trial will be invited for every follow-up visit according to schedule until he/she withdraws.

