#### **15.General Reporting Requirements**

Complications (Adverse events) reporting are an investigator's responsibility to assess and report. Adverse Events (AE) will be identified and captured on the electronic Complications eCRF

throughout the duration of the study as they occur and will be followed until they are adequately resolved or explained. Any Serious Mesh-Related Adverse Events with Clavien-Dindo Classification 3b or more should be reported to primary investigation site without delay after the site first learns of the event.

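### Protocol section 13 lets the investigator take a patient out of the study for wellbeing, which appears to end outcome and safety follow-up although closure is already complete

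*Protocol*

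**What the plan says.** Section 13 of the protocol covers withdrawal and discontinuation in one paragraph.

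- It first gives the patient or representative the right to withdraw, then defines the consequence: "withdrawal means the subject is no longer participating in the study and no further study-related follow-ups will be performed".
- It asks for an evaluation at the time of withdrawal and for efforts to document the outcome then. It adds: "Data collected until withdrawal will be analyzed".
- It then gives the investigator a separate power: "The investigator has the right to discontinue subjects from the study at his/her discretion to ensure wellbeing of the subject". The only criterion is wellbeing.
- The next sentence reads: "The reasons for withdrawal shall be documented (electronic Patient Withdrawal Request Form").

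Section 13.1 states: "Each patient in the trial will be invited for every follow-up visit according to schedule until he/she withdraws".

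Section 15 says that adverse events are captured "throughout the duration of the study as they occur and will be followed until they are adequately" resolved or explained. Section 4 gives long-term results and safety as the purpose of follow-up to 5 years.

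Section 10.3 (Study Plan) names national registers that "may be used to collect data of patients' survival and operations done to patient outside study sites".

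**The concern.** In a trial of continuing treatment, an investigator may need to stop the treatment for a patient's sake. Here the studied intervention is a single act, closure of the abdomen with or without mesh at the end of the index operation (section 14.2). What remains of the study is a telephone assessment at 30 days, clinical visits, ultrasound, CT where needed, and questionnaires. Taking a patient out of the study after surgery therefore stops no study treatment. It stops mainly observation.

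The stated ground is wellbeing, so use of the power may be related to a poor course and hence to outcome. If study follow-up ends with it, later complications, re-operations and 2- and 5-year hernia status can be lost in patients whose results matter to the safety and efficacy conclusions. Section 9.1 adds to this. The second safety review is timed and described by patients who have reached 2 years, and discontinuation of the trial is tied to complications at 30 days or 2 years. A patient discontinued before 2 years may not be counted there.

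**Working it through.** **Does investigator discontinuation end follow-up?** The sentence that ends follow-up is worded for withdrawal. Three features extend it to the investigator's power: that power removes the patient from the study rather than from a treatment, it stands in the same paragraph, and the next sentence calls the reasons withdrawal reasons and puts them on the withdrawal form. Two features point the other way: section 13.1 ties the end of invitations to the patient's own withdrawal, and the Study Closure Form footnote in section 12 lists loss to follow-up, consent withdrawal and completion, but not investigator discontinuation. The inference is strong, but it remains an inference.

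**Where the sections collide.**

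| Situation | Section 13, so read | Other section |
|---|---|---|
| Adverse event still open at discontinuation | No further study follow-up | Section 15: follow until resolved or explained |
| Complication arising later | Not collected by the study | Section 15: capture for the study's duration; section 4: safety to 5 years |
| 2-year safety review | Patient may never reach 2 years | Section 9.1: review described by patients who reached 2 years |

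**What is kept.** Data up to withdrawal and an evaluation at that time. A complication or hernia already documented is therefore counted. The registers are optional and cover survival and operations outside the study sites. They do not give ultrasound hernia status, quality of life or complications managed without an operation. Multiple imputation is planned for sensitivity analysis only (section 19.3).

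**The plan's own figure.** Section 19.1: 10% hernia with mesh, 25% in controls, alpha 0.05, power 80%. The unpooled normal approximation, two-sided, gives n = (1.960 + 0.842)² × (0.25×0.75 + 0.10×0.90) / 0.15² = 96.8, so 97 per group. With 20% dropout, 97/0.8 = 121.25, so 122. Both stated figures reproduce.

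**Illustration for hernia.** Assume that a share f of patients who have or would get a hernia is discontinued before it is documented and analysed as missing. The protocol gives no value for f; 10% to 30% is an assumed range. The observed rate is p(1 − f)/(1 − pf).

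| f | Control 25% seen as | Mesh 10% seen as | Difference, both arms | Mesh arm only | Control arm only |
|---|---|---|---|---|---|
| 0% | 25.0% | 10.0% | 15.0 | 15.0 | 15.0 |
| 10% | 23.1% | 9.1% | 14.0 | 15.9 | 13.1 |
| 20% | 21.1% | 8.2% | 12.9 | 16.8 | 11.1 |
| 30% | 18.9% | 7.2% | 11.7 | 17.8 | 8.9 |

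Differences are in percentage points. With 97 analysed per arm and loss in both arms, power by the pooled formula falls from 79% to 76%, 72% and 68%. With 25% hernia in both arms and loss in the mesh arm only, a spurious benefit of 1.9, 4.0 and 6.1 points appears.

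These losses are small in number. At f = 30% they are 0.30 × 25% = 7.5% of controls (about 9 of 122) and 0.30 × 10% = 3% of mesh patients (about 4 of 122). Both fit within the 20% allowance (122 − 97 = 25 per group), so they would not by themselves trigger the sample size recalculation foreseen in section 19.1.

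**Illustration for late harm, in either arm.** Assume 5% of an arm is discontinued, with later-harm risk 50% in them and 5% in the rest. The true rate is 0.05×0.50 + 0.95×0.05 = 7.25%; 5.0% is observed, so 2.25/7.25 = 31% of the harm is missed. At 10% discontinued: 0.10×0.50 + 0.90×0.05 = 9.5% against 5.0%, so 4.5/9.5 = 47% is missed. All three inputs are assumptions.

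**The case against.** The fair defence is that section 13 is loosely worded rather than wrong. The end of follow-up is attached to the patient's withdrawal, and sections 12 and 13.1 can be read the same way. The investigator's power is discretionary while section 15 is a duty, so a site can satisfy both by not using the power while an event is open. The protocol also records mesh removals, re-operations and complications as outcomes, and section 10.3 (Blinding) gives access to the allocation when complications occur. Nothing suggests that such patients are meant to leave the study.

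Much of this stands. A reader might infer that the clause will remove patients with mesh infection, fistula or mesh removal and so make mesh look safer and more effective. The protocol does not support that. It names no such trigger, the power covers both arms, and loss in the control arm or in both arms moves the hernia difference the other way. A reader might also infer that a site can never comply with sections 13 and 15 together. The conflict is direct only when a patient is discontinued with an event open. Nor can imputation be said to fail, because no imputation model is given here.

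The defence does not show that follow-up continues after investigator discontinuation. No sentence says so, and the natural reading of the paragraph is that it stops.

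**Conclusion.** The point holds as a flaw in a stated rule that should be corrected. Section 13 gives a power whose apparent effect is to stop outcome and safety observation after a one-time intervention, on a ground that may be related to outcome. It conflicts with section 15 when an event is unresolved and with the 5-year safety purpose in section 4, and it may remove patients from the 2-year safety review.

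The loss is limited to events after discontinuation and to 2- and 5-year hernia status. The protocol does not say how often the power would be used or in which arm, so neither the size nor the direction of bias can be determined. The calculations show only what assumed losses would do. For hernia, even the assumed range leaves a sizeable difference between arms. Late safety is the stronger reason to act, since rare late events depend on the few patients who do badly. The conclusion rests on reading investigator discontinuation as a form of withdrawal. If that is not intended, the text needs to say so.

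**What to change.** In section 13, separate the patient's withdrawal of consent from discontinuation by the investigator. State that scheduled outcome and safety follow-up continues after investigator discontinuation unless the patient refuses it.

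Bring section 12 (closure form reasons), section 13.1 (invitations) and section 15 (adverse event follow-up) into line with this. In section 10.3 (Study Plan), make register use definite instead of optional for survival and re-operations, in patients who have not refused use of their data.

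The cost is amendment wording, consent and register-permission wording, and a register request that the protocol already foresees. No visit is added to the schedule, although patients who would otherwise have left would attend the visits already planned. The wellbeing provision can remain. Only its consequence for follow-up needs to be stated, and no clinical rule is proposed.

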#### 13.1 Subject lost to Follow-up

The investigator will attempt to contact the subject at least three times prior to designating them as lost to follow-up. The patient who may hesitate to come to follow-up visit, are asked to return the PROMIS questionnaire to estimate the risk of incisional hernia (48).

The investigator will

document the date and type of attempted communication. If a subject cannot be reached during the visit window, a missed visit will be recorded. Each patient in the trial will be invited for every follow-up visit according to schedule until he/she withdraws.

### 14 Procedures

#### 14.1. Perioperative care

Perioperative care includes the assessment and optimization of medical risk factors and standard anesthesia. Antibiotic prophylaxis is accomplished according to the hospital protocol and routine practice.

Postoperative treatment at the surgical ward is accomplished according to the standard protocol.

#### 14.2 Wound Closure technique

At the end of the operation, the abdomen will be closed according to patient's randomization group if applicable.

In the mesh group, the posterior layer of rectus sheath is opened as close to midline as possible

without interrupting the midline. The space behind the rectus muscle is created mainly using blunt dissection. At each ends of the incision, opening of the retrorectus space is reached both cranial

and caudal over the ends of the wound, if applicable. The posterior layer is closed using 0 or 2-0

slowly absorbable monofilament 4:1 small stitch technique. The stitch bites are 5 mm with 5mm

interstitch space. The length of the wound is measured, as well as the length of suturing material

used. The aim is to close using suture material at least four times the length of the wound (4:1) by small stitch technique. After securing there will be no contact with the mesh and abdominal

cavity, 8 cm wide self-gripping mesh (Progrip™, Medtronic) is applied on the posterior layer of the rectus sheath, reaching over the opening at each end. The anterior layer of rectus sheath is closed using slowly absorbable monofilament USP 2-0 or 0 suture by 4:1 small stitch technique. The

length of the mesh and suture material used are measured. Subcutaneous layer will be left open if contamination class is 4. The subcutaneous layer may be left temporary with VAC or other wound dressing according to surgeons' preference. In contamination classes 1-3, the skin is closed

according to surgeons' preference.

In case the mesh cannot be safely kept outside the abdominal cavity, patient is intra-operatively excluded.

PREEMER TRIAL 27

In the no mesh group, the rectus aponeurosis is closed in a single aponeurotic layer by using slowly absorbable monofilament USP 2-0 or 0 suture by 4:1 small stitch technique. Both the length of the wound and length of the suture material used is measured.

Catalogue of the operative technique will be sent to all participating surgeons to standardize the procedure.

#### **14.3 Postoperative treatment**

Postoperative treatment will be accomplished according to standard protocol of each participating hospital.

#### **14.4. Mesh (ProgripTM, Medtronic)**

A standard 8 cm self-gripping prophylactic mesh will be used in mesh group. The width of the mesh is standard. The length of the mesh is measured and reached over both ends of the laparotomy opening.

#### **15.General Reporting Requirements**

Complications (Adverse events) reporting are an investigator's responsibility to assess and report. Adverse Events (AE) will be identified and captured on the electronic Complications eCRF

throughout the duration of the study as they occur and will be followed until they are adequately resolved or explained. Any Serious Mesh-Related Adverse Events with Clavien-Dindo Classification 3b or more should be reported to primary investigation site without delay after the site first learns of the event.

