## 6.2 Secondary Endpoints

Secondary Endpoints:

- Comprehensive Complication Index within 30 days from surgery
- Surgical site infection (SSI) rate defined by CDC classification of surgical site infection  
within 30 days follow up
- Fascial rupture within 30 days from surgery
- Incidence of Incisional hernia within 5 years follow-up
- Incisional hernia repair rate within 2 and 5 years after surgery
- Re-operations due to mesh- or hernia within 2 and 5 years from surgery
- Quality of life (RAND-36, AAS, PROMIS) within 30 days, 2 and 5 years from surgery
- Medico-economic explorative measures
  - Time to create the retrorectal space and insert the mesh
  - Length of stay
  - Costs of materials used to close the abdomen
  - Length of sick leave

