## 9. Risk Analysis

### 9.1. Potential Risks

Surgeons performing emergency laparotomies will be trained and guided for the mesh placement. Based on previous studies, the use of the mesh is both safe and effective.

Study patients will be

followed very closely postoperatively.

As the previous research on synthetic mesh utilized as prophylaxis at emergency midline laparotomy is scarce, an analysis of the complications and risks is done and evaluated for safety

reasons after 30 patients have been randomized to each group and reached 30 days follow-up. For the same reason, there will be further analysis on the complications of the mesh after 30 patients randomized to each group have reached the 2 years follow-up.

If there are significantly more-serious complications in either group compared to other at 30 days or 2 years control, the trial will be discontinued.

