## 10.3 Blinding

Study patients will be blinded of the randomization group during the whole follow-up period.

Both the surgeon evaluating the outcome at 30 days, 2- and 5- years control as well as radiologist will

be blinded of the randomization group. The method of fascial closure (i.e. the allocated procedure) will not be revealed in medical records. In both groups, the following sentence will be

written in the medical records: "Fascial closure was performed according to randomization group". Patients randomization number will be available in medical records. Envelopes marked with randomization number containing allocated group information are accessible at all times in

case of complications or other need to know the allocated group. A record of unsuccessful blinding will be maintained and published.

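### The re-operation endpoint and the 2-year safety look depend on an undefined attribution to mesh, which only one arm can have

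*Protocol*

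**What the plan says.** Four places in the Protocol bear on this.

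- **Section 6.2** (and the synopsis) lists the secondary endpoint "Re-operations due to mesh- or hernia within 2 and 5 years from surgery". The incisional hernia repair rate is a separate endpoint. The Comprehensive Complication Index, surgical site infection and fascial rupture are endpoints at 30 days only.
- **Section 9.1** (and the synopsis) plans two safety looks, each with 30 patients per group. For the first, at 30 days, "an analysis of the complications and risks is done and evaluated for safety". For the second, "there will be further analysis on the complications of the mesh after 30 patients randomized to each group have reached the 2 years follow-up". It then adds: "If there are significantly more-serious complications in either group compared to other at 30 days or 2 years control, the trial will be discontinued".
- **Section 15** states that "Adverse Events (AE) will be identified and captured on the electronic Complications eCRF" for the whole study, without limit by arm or cause. Immediate notification is narrower: "Any Serious Mesh-Related Adverse Events with Clavien-Dindo Classification 3b or more should be reported to primary investigation site without delay".
- **Section 10.3, Blinding**, keeps the allocation from "Both the surgeon evaluating the outcome at 30 days, 2- and 5- years control as well as radiologist" and keeps the closure method out of the medical records. Allocation envelopes can be opened when complications arise.

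The Protocol does not define mesh-related. It does not say who makes the attribution, or whether this is done before or after an envelope is opened.

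**The concern.** A between-arm comparison needs an event that can occur, and be recognised, in both arms. A re-operation due to mesh fails that test by definition. Take a re-operation for deep wound infection a year after surgery. In the mesh arm it may be put down to the mesh and counted. In a control it is neither mesh nor hernia, so it falls outside the endpoint.

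The same difficulty affects the 2-year look if its wording is taken literally: complications of the mesh cannot be compared with a group that has no mesh.

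The Protocol treats the safety of mesh in emergency surgery as an open question (Sections 2.4 and 9.1). The question is whether mesh adds harm to the wound complications that emergency laparotomy causes anyway. A count confined to mesh-attributed events cannot answer it.

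**Working it through.** The Protocol gives no figure on this point, and its sample size is not in dispute. The check sets the passages side by side and then shows how the error depends on attribution.

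**1. Which safety elements need attribution to mesh?**

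| Element | Attribution needed? | Can controls contribute? |
|---|---|---|
| Adverse events on the eCRF (Section 15) | No | Yes |
| 30-day look (Section 9.1) | No | Yes |
| Complication index, infection, fascial rupture at 30 days (Section 6.2) | No | Yes |
| Stopping sentence, 30 days and 2 years (Section 9.1) | No | Yes |
| 2-year look as worded (Section 9.1) | Yes | Not if read literally |
| Re-operation endpoint, hernia part (Section 6.2) | No | Yes |
| Re-operation endpoint, mesh part (Section 6.2) | Yes | No |
| Prompt reporting (Section 15) | Yes | No |

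Of the three elements that need attribution, the first two bear on a comparison and the third on notification only.

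**2. Does another endpoint catch the late re-operation?** The three general complication endpoints in Section 6.2 end at 30 days. The infection table in Section 11.3 mentions 30 or 90 days for deep and organ/space infection, but even 90 days leaves most of the 2 and 5 years uncovered. The repair rate covers hernia only. So no other listed endpoint captures a late re-operation for wound infection.

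**3. Size of the error in the re-operation endpoint.** Let h be the proportion re-operated for hernia and w the proportion re-operated for a wound or abdominal-wall problem other than hernia. Subscripts m and c denote mesh and control, and for simplicity no patient has both. Let s be the share of the mesh arm's w that is attributed to mesh.

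- As worded: difference = (h_m + s·w_m) − h_c.
- Cause-free: difference = (h_m + w_m) − (h_c + w_c).
- Error = first minus second = w_c − (1 − s)·w_m.

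The hernia part cancels. The Protocol gives neither w nor s, so the values below are assumptions:

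| w_m | w_c | s | Error (percentage points) |
|---|---|---|---|
| 5% | 5% | 0 | 5 − 5 = 0 |
| 5% | 5% | 0.5 | 5 − 2.5 = +2.5 |
| 5% | 5% | 1 | 5 − 0 = +5 |
| 10% | 5% | 0 | 5 − 10 = −5 |
| 10% | 5% | 0.5 | 5 − 5 = 0 |
| 10% | 5% | 1 | 5 − 0 = +5 |

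With no true effect, any attribution produces an apparent excess in the mesh arm. With a true excess, sparse attribution hides it and full attribution exaggerates it.

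**4. The 2-year look, extreme case only.** Suppose mesh-attributed counts were fed into the comparison, every serious event in the mesh arm were so labelled, and the test were Fisher's exact at two-sided 0.05 (the stopping sentence names no test or level). Controls then score 0 of 30. The smallest significant mesh count is 6 of 30: p = 2 × C(30,6)/C(60,6) = 2 × 593,775/50,063,860 = 0.024. With equal true rates in both arms, the chance of 6 or more among 30 is 7% at a true rate of 10% and 57% at 20%. If all serious events in both arms are counted, the chance of a significant difference in either direction is 0.9% and 2.2%. The stopping sentence as written asks for the second kind of count, which is why the wording of the look should match it.

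**The case against.** The strongest reply is that the decision rule is already sound. The stopping sentence compares serious complications in both arms at both looks, with no reference to cause. The 2-year look takes patients from each group and is introduced for the same reason as the general 30-day look, so a comparative analysis may well be what is meant. Section 15 governs notification and removes no control event from any dataset. The synopsis lists procedure-related re-operations among the follow-up data, so a control re-operated for infection would be recorded. Controls also contribute hernia re-operations to the composite. Secondary outcomes are declared hypothesis generating (Section 19.1).

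Most of this stands, and it rules out three stronger readings that a reader might infer:

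- **That the whole safety comparison is one-sided.** The first table under the working shows that most elements need no attribution.
- **That attribution cannot be judged at all.** The blinding covers the outcome surgeon and the radiologist. Envelopes may be opened for complications, mesh removals are recorded, and failures of blinding are logged. What remains is that attribution requires knowing the arm, and the Protocol does not say how that is handled.
- **That counts such as 6 v 0 show the bias to be expected.** With 122 per arm that split gives p = 0.029, but it assumes full attribution and a rate not in the Protocol. It also omits the hernia re-operations that controls contribute; 5 v 0 already gives p = 0.060.

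The reply does not rescue the endpoint definition, since recording an event is not the same as counting it. Nor does it make the wording of the 2-year look agree with the sentence that acts on it.

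**Conclusion.** The point holds for two elements. The re-operation endpoint has a component that cannot occur in controls, and no other listed endpoint covers the gap after 30 days. The 2-year look is described as an analysis of mesh complications beside a stopping sentence that compares the groups on serious complications; these passages must be reconciled.

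The prompt-reporting trigger is a lesser matter. The primary site hears sooner of mesh-arm events, and reporting depends on knowing the allocation, but the analysed data are not changed.

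The size cannot be fixed from the Protocol. Under the assumed rates, the error in the endpoint runs from −5 to +5 percentage points, depending on the share attributed to mesh and on whether mesh adds real harm. The primary endpoint and the sample size are unaffected. This should be corrected, but it does not undermine the trial.

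**What to change.** - **Section 6.2 and synopsis:** make the compared endpoint all re-operations on the wound or abdominal wall, including hernia repair, at 2 and 5 years in both arms and regardless of cause. Describe mesh removal and mesh-attributed events separately, for the mesh arm only. State who attributes an event and whether the allocation is known at that time.
- **Section 9.1 and synopsis:** word the 2-year look as an analysis, in both arms, of the same cause-free set of serious complications that the stopping sentence already compares.
- **Section 15:** reconcile the prompt-reporting trigger with that event set, so that notification does not depend on the arm.

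The cost is minor wording in the Protocol and eCRF and some more prompt reports from control patients. Complications are already recorded in both arms. The drawback is a less mesh-specific endpoint, which the separate mesh-arm description partly makes good.
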